**FORM: Application for Human Research**

NUMBER	FORM DATE	PAGE
F200		7 of 18

fascia uniformly along with 68% of patients with CPF reporting central band tenderness as opposed to 26% having lateral band tenderness. In addition to the evidence of inflammation, the presence of a hyper-echoic lesion in the plantar fascia was noted in 68% to 84% of patients with CPF. Diagnostic ultrasound has also been used to quantify the effectiveness of treatments such as extra-corporeal shock wave therapy, NSAIDs and Botox injections for subjects with CPF.

More than twenty different treatments have been used for plantar fasciitis. The combination of rest, ice, stretching and NSAIDs are used as initial management in most patients and have been shown to effectively treat symptoms in 90% of patients in less than 12 months. However, 10% of patients fail conservative management and continue to have symptoms beyond 12 months (termed refractory plantar fasciitis or RPF). Surgery consisting of partial plantar fascia release or gastrocnemius recession is often considered in these patients. However, the outcomes of surgery are not uniformly positive with 50% of patients reporting residual symptoms. Moreover, evidence supporting surgical treatment of RPF is weak as there are no randomized controlled trials comparing its efficacy to other treatments. Thus, for many patients the risks of surgery such as arch instability, prolonged wound healing, and longer rehabilitation times simply outweigh the benefits. Is there a non-invasive treatment that can be used as an adjunct to speed healing in patients with CPF and as an alternative to surgery in those with RPF? The primary objective of this study is to evaluate the efficacy of combining the non-invasive treatment with intense therapeutic ultrasound (ITU) with standard care for the treatment of chronic plantar fasciitis. A secondary objective is to evaluate the tolerability and safety of intense therapeutic ultrasound in the treatment of plantar fasciitis.

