**FORM: Application for Human Research**

NUMBER	FORM DATE	PAGE
F200		8 of 18

3) Setting of the Human Research

The PI is an assistant professor in the Department of Orthopaedic Surgery and surgeon with the University of Arizona Health Network. Subjects will be recruited from the outpatient clinic of Drs. [name] (PI) and [name]. The age, gender, height, weight, activity level, pain level, and physical exam findings of patients will be obtained directly from the subject, the subject's medical record, or from direct examination and then recorded in a password protected excel file. The online survey can be completed from any computer available to the subject. Intense therapeutic ultrasound and diagnostic ultrasound will be administered in the Human Movements Biomechanics Lab (BRL B101).

4) Resources available to conduct the Human Research

Equipment for intense therapeutic ultrasound will be provided by [name] and [name] from Guided Therapy Systems. The equipment for measuring height and weight will be in the orthopedic clinic. Personnel available to conduct the study include 2 surgeons, 1 clinical research coordinator, 2 sonographers, 1 medical student, and 2 undergraduate assistants. These individuals will be available to recruit and consent patients, coordinate and conduct the study, analyze the data, and produce a manuscript.

5) Study Population

Male and female adults (18 years or older) with plantar heel pain and point tenderness near the medial calcaneal insertion of the plantar fascia for at least three months without improvement will be considered for inclusion into the study. Subjects with diabetes, bilateral plantar heel pain, current systemic or local infection, previous foot surgeries, other foot/ankle pathologies (inflammatory arthritis, gout, neurologic disorders, connective tissue disorders and malignancy), contraindications to the use of NSAIDs, and pregnancy will be excluded. The target enrollment of this pilot study is 50 participants.

6) Recruitment Methods and Consenting Process

Subjects will be recruited utilizing public media, list serves, community organizations, and via referral. Please see the attachments to this application for an electronic media and brochure representations of the advertisements to be utilized. We would like to select from the following wording to produce recruitment materials -

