Interested individuals who contact the laboratory will have the logistics of the study explained and be referred to the clinic for diagnosis and treatment of heel pain. All patients diagnosed with plantar fasciitis by participating physicians will be contacted by the research team to discuss the details associated with participation. We would like to obtain a temporary deferment of authorization to obtain contact information from the electronic medical record for those individuals who are initially identified in the clinics by participating physicians. Additionally, we would like permission to provide the consent and authorization forms and other information by e/mail should this be conducive to obtaining informed consent. The mailing is for informational purposes only to allow the subject more time to consider participation in the study. The informed consent process will be completed in person. Both English and Spanish versions of the consent forms will be utilized, although the Spanish consent form will be submitted as a modification once the English version is approved. Finally, we would like to provide a map and information sheet to assist participation in the study (see attachments).

7) Procedures involved in the Human Research

After obtaining informed consent and authorization from the subject, study personnel will verify the screening of participants utilizing the inclusion/exclusion criteria and collect the following information- age, gender, height, weight, activity level, pain level, and physical exam findings including x-rays - which will be recorded on the data abstraction sheet (see attachment). The activities strictly associated with the research are the assignment to a study group (Control or ITU), the administration of patient reported outcome measures (questionnaires), and therapeutic and/or diagnostic ultrasound (Table 1). Additionally, adverse events will be recorded at each visit (see attachment). Treatment tolerability will be prior to, immediately after, and at 2 days post-treatment.

Standard of care is integrated into both arms of the investigation and includes a structured physical examination, the use of an NSAIDs for 3 weeks (Naprosyn 500 mg po bid or Ibuprofen 800 mg po tid taken with meals), viscoelastic heel cups for 12 weeks, and supervised physical therapy with home exercise program for 6 weeks. These components are described below-

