Randomization and Blinding. Suitable subjects will be randomly assigned (1:1) to receive standard of care with a sham ultrasound treatment (Control group) or standard of care + ITU treatment (ITU group) by the application of an algorithm (e.g. even vs odd) to the number provided by a random-number generator. Most members of the research team and the subject will be blinded to group assignment. Only the clinical research coordinator and ultrasound treatment team will be privy to the subject's group assignment.

Patient Reported Outcome Measures (Aim 1). The principal aim of this study is to compare the efficacy of treatment and time course of response to treatment between the two groups using validated

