Assessment of Safety and Tolerability (Aim 3). Subject self-assessments of treatment tolerability will be conducted immediately after, two days after (phone survey) and two weeks after treatment using a 10-point visual analog scale (VAS, see Appendix 1-C). The subject will be asked to report their current level of pain and the maximum level of pain experienced over the last two days. The VAS is the standard for assessing pain for both clinical and research purposes. Recording of adverse events will take place at all visits (see adverse event reporting form Appendix 4 in the protocol). Adverse events and serious adverse events will be monitored throughout the study. A treatment will not be administered if there is residual pain/discomfort experienced by the subject from the previous treatment.

Statistical analysis. Data will be assessed for variance homogeneity and normality. FFI-P, PFCAT, and FAAM scores before and after intervention will be compared between the two groups using a paired t-test. Additionally, the mean thickness of the plantar fascia will be compared between the two groups before and after treatment and significance determined utilizing paired t tests. P<0.05 is considered to be statistically significant.

8) Risks to subjects

Exposure to ITU may produce short-term sensations which may cause discomfort and mild erythema for up to a few hours following the exposure. No detrimental side effects have been reported in previous clinical trials investigating similar devices in which ultrasound energy was applied to the neck and face. Additionally, the ITU in this investigation will utilize lower power parameters than those reported for these similar devices. We are seeking classification of the GEN II system (Guided

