## Statistical Approach

- Pain Reduction:

Pain level at the plantar fascia was self-reported by subjects at pre-treatment (used as baseline measurement) and again at each follow-up - 4, 8, 12, and 26 weeks - after initial treatment. The pain scale subjects used to identify their level of pain was a 10-point pain scale range, where 0 = no pain, 1 = slight pain through 10 which equates to the patient's worst imaginable pain. The goal for all subjects in the treatment group was to reduce pain by at least 25%. Pain scores reported at follow-up timepoints were compared to baseline score for each subject to determine if the goal was met by dividing the difference in the follow-up and baseline pain score by the baseline pain score. The percentage of subjects that met the pain reduction goal was calculated at each timepoint for both control/sham-treated and treatment groups by dividing the number of subjects that achieved the pain reduction goal at each timepoint by the total number of patients that gave a pain score for that time point.

- Plantar Fascia Hypoechoic Lesion Size:

A large proportion of patients suffering from chronic plantar fasciitis present with hypoechoic lesions in or around the proximal plantar fascia, as viewed by diagnostic ultrasound imaging[7].

Hypoechoic lesions were imaged and volumes were calculated at the baseline visit and each follow-up visit by measuring the inferior-to-superior and posterior-to-anterior radii in the long axis and the medial-to-lateral radius of the transverse axis and applying the following formula for the volume of an ellipse:

$$\text{Volume} = (4/3)\pi \cdot r_1 \cdot r_2 \cdot r_3$$

With  $r_1$ ,  $r_2$ , and  $r_3$  representing the three radii detailed above. Changes to lesion volumes were recorded at each follow-up timepoint and compared to baseline by dividing the volume of the lesion at that timepoint with the volume of the same lesion at pre-treatment baseline.

- Foot Function Index Score Reduction:

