In addition to the 11-point VAS pain scale, patients self-reported answers to questions from the Foot Function Index (FFI) pain subscale questionnaire, which has been standardized in a number of PF-focused publications [8-10]. Scores range from 0-90, with 0 indicating no pain and 90 indicating the worst pain imaginable in a variety of daily activities involving use of the plantar fascia. Self-reported scores were taken at baseline and each follow-up timepoint. The average score for each timepoint were calculated, and follow-up averages were compared to baseline to calculated the percentage reduction in score.

- Statistical Calculations

Student T-tests were utilized to determine statistically significant differences between baseline and subsequent follow-up measurements for self-reported and lesion size measurements. The level of significance ( $\alpha$ ) was set to 0.05.

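### The SAP gives no ITU-versus-sham test or interval, only baseline-versus-follow-up t-tests, and the protocol names a paired t-test for two unpaired arms.

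*SAP*

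**What the plan says.** **Aim.** Aims 1 and 2 (protocol Section 3, Background) set standard care plus ITU against standard care plus sham, for patient-reported outcomes and for fascia thickness. Under Patient Reported Outcome Measures the protocol adds: "The principal aim of this study is to compare the efficacy of treatment and time course of response to treatment between the two groups". The Randomization and Blinding paragraph allocates individual subjects 1:1 and describes no matching. Study Population excludes bilateral heel pain, so a subject's two feet cannot serve as a pair either.

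**Protocol test.** The Statistical analysis paragraph says: "FFI-P, PFCAT, and FAAM scores before and after intervention will be compared between the two groups using a paired t-test". For thickness it says that "the mean thickness of the plantar fascia will be compared between the two groups before and after treatment and significance determined utilizing paired t tests".

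**SAP tests.** Statistical Calculations holds the only inferential sentence: "Student T-tests were utilized to determine statistically significant differences between baseline and subsequent follow-up measurements for self-reported and lesion size measurements". It does not say whether these tests are run within each arm or pooled, or whether they are paired. FFI averages and lesion volumes are related to baseline only, with no mention of arm. One output is by arm: "The percentage of subjects that met the pain reduction goal was calculated at each timepoint for both control/sham-treated and treatment groups". No difference, interval or test accompanies it.

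**The concern.** A significant change from baseline in the ITU arm combines any ITU effect with standard care, natural history, regression to the mean and the response to sham. The sham arm is there to remove those components, and the SAP's tests never use it as a comparator.

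Improvement without ITU is to be expected. "Standard of care is integrated into both arms of the investigation", and it comprises NSAIDs, heel cups and physical therapy. The Background says that rest, ice, stretching and NSAIDs "have been shown to effectively treat symptoms in 90% of patients in less than 12 months". The rate may well be lower here, since entry requires heel pain "for at least three months without improvement will be considered for inclusion into the study", and follow-up ends at 24 or 26 weeks. Some shared improvement remains likely.

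At stake is the main conclusion of the trial. Standard care alone could produce significant p-values in the ITU arm, and a real ITU effect could go undemonstrated because both arms improve significantly.

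**Working it through.** **1. What each statement can test**

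| Statement | Contrast | ITU-versus-sham inference? |
|---|---|---|
| SAP, Statistical Calculations | follow-up against baseline | none |
| SAP, Pain Reduction | responder percentage in each arm | descriptive only |
| SAP, lesion size and FFI | ratio or percentage against baseline | none |
| Protocol, Statistical analysis | between groups, by paired t-test | none valid as named |

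The protocol sentence has two readings. If it means before/after tests within each arm, there is no between-arm test. If it means a comparison of change scores, the intent is sound but the test is an independent-samples t-test and is misnamed. Both readings need correction.

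**2. Inputs for the illustration**

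- From the documents: target enrolment 50, 1:1 allocation, significance level 0.05.
- Assumed: 25 per arm with no dropout, two-sided tests, per-arm paired t-tests, and effects expressed in SDs of the change score. The documents give no SD, effect size or sidedness, and no power calculation to reproduce.

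**3. No ITU effect, same improvement d in both arms**

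The paired test in one arm has a noncentral t distribution with n − 1 df and noncentrality d√n. For n = 25 the noncentrality is 5d and the critical value is 2.064. Call its power p. The arms are independent, so the chance that ITU is significant and sham is not is p(1 − p).

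| d | 5d | p (ITU arm significant) | p(1 − p) | pooled test, n = 50 |
|---|---|---|---|---|
| 0.3 | 1.5 | 0.302 | 0.302 × 0.698 = 0.211 | 0.548 |
| 0.5 | 2.5 | 0.670 | 0.670 × 0.330 = 0.221 | 0.934 |
| 0.8 | 4.0 | 0.970 | 0.970 × 0.030 = 0.029 | 0.9998 |

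A valid two-sided 0.05 test would favour ITU falsely in 2.5% of trials. Reading significance in ITU but not in sham as efficacy would do so in 21%, 22% and 3%. The documents do not state that rule, but their tests leave a reader little else to compare.

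**4. A real ITU effect that the baseline tests do not show**

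Take 0.8 SD shared improvement and a further 0.8 SD from ITU. The sham arm is significant with probability 0.97 and the ITU arm almost always, so both are significant in 97% of trials and the tests show no contrast. An independent-samples t-test on change (noncentrality 0.8 × √(25/2) = 2.83, 48 df) has 79% power.

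**5. Responder percentages without an interval**

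With equal true rates π in both arms, 25 per arm and exact binomial probabilities, the chance that ITU exceeds sham by at least 5 patients (20 points) is shown below. The 95% CI half-width is 1.96√(2π(1 − π)/25).

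| π | P(gap ≥ 20 points favouring ITU) | half-width |
|---|---|---|
| 0.5 | 0.101 | 0.277 |
| 0.6 | 0.097 | 0.272 |
| 0.7 | 0.082 | 0.254 |
| 0.8 | 0.055 | 0.222 |
| 0.9 | 0.017 | 0.166 |

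**The case against.** The strongest reply is that the plan does intend a between-group comparison. The protocol says so, the SAP shows responders for both arms, and nothing says the SAP replaces the protocol's paragraph. The study also calls itself a pilot. The intent is real, but no valid procedure carries it out: the protocol's named test does not apply to unmatched arms, and it does not cover the SAP's responder or lesion-volume outcomes. Pilot status does not excuse the gap either, because efficacy is the primary objective and both documents set a 0.05 significance level.

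The figures are open to fair criticism:

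- The SD values have no source in the documents, and at 0.8 SD the 3% error rate is close to the nominal 2.5%.
- Pooling is hard to read into the pain analysis, which separates the arms. It is an open question only for FFI and lesion volume.
- Even/odd assignment from random numbers does not guarantee 25 per arm, missing scores would reduce the numbers, and not every subject will have a lesion.

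These points limit how far the illustration can be pressed. They do not touch the omission, which is established from the text alone.

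**Conclusion.** The concern holds and must be fixed. No sentence in the SAP provides inference on ITU versus sham, and the protocol's sentence names a test that cannot provide it. The reading of the protocol sentence, misnamed or purely within-arm, stays open; the need to correct it does not.

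The size depends on the assumptions in the working. With no ITU effect, the ITU arm's baseline test would be significant in 30% to 97% of trials as shared improvement goes from 0.3 to 0.8 SD. A 20-point responder gap favouring ITU would arise by chance in about 10% to 5% of trials at true rates of 50% to 80% (2% at 90%). The matching 95% CI half-widths are about 28 to 22 points (17 at 90%), which a reader of two bare percentages cannot see.

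**What to change.** Replace the test statements in the protocol's Statistical analysis paragraph and the SAP's Statistical Calculations with one between-arm statement, for example:

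> For each continuous outcome, follow-up values will be compared between the randomised ITU and sham arms with adjustment for the baseline value, using a mixed model over post-baseline visits with arm, visit and arm-by-visit terms. The ITU minus sham difference at each reported visit will be given with its 95% confidence interval.

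ANCOVA at each reported visit is an acceptable alternative, and an independent-samples t-test on change from baseline is the minimum cure. Choose one method and name it before any rerun, so that the choice does not follow the results. For lesion volume, which the SAP expresses as a ratio to baseline, state the scale of analysis as well.

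For the 25% pain-reduction endpoint, report the risk difference with a 95% CI and an exact test at each reported visit. Present changes from baseline by arm, descriptively and without p-values.

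**Cost.** No new measurements are called for, since baseline and follow-up values in both arms are already planned. The SAP never mentions fascia thickness, PROMIS PF CAT or FAAM, so confirm that those data exist. Because the SAP is written in the past tense, the change must be dated and disclosed, and any completed analysis rerun. The statement must also name its visits: the SAP lists 4, 8, 12 and 26 weeks, and the protocol lists 2, 4, 6, 12 and 24 weeks after baseline.

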The purpose of this study is to assess the effectiveness of ITU in the treatment of CPF by comparing pain, function, and change in plantar fascia thickness in subjects treated with ITU in addition to standard of care to subjects that are treated with standard of care alone. The primary outcome measure will be a computer adaptive questionnaire where pain, function and level of activity will be compared between the two groups. In addition, with the use of diagnostic ultrasound, plantar fascia thickness and presence or absence of hyper-echoic lesion will be compared between the two groups. Finally, the safety and tolerability of ITU will be monitored through the course of the study. It is hypothesized that patients receiving ITU in addition to standard of care will have a more rapid resolution of their pain, faster return to activities, and a greater decrease in plantar fascia thickening on ultrasound as compared to those only receiving standard of care.

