**FORM: Application for Human Research**

NUMBER	FORM DATE	PAGE
F200		11 of 18

patient reported outcome measures assessing pain, function and level of activity. Subjects will complete validated patient reported outcome questionnaires assessing pain, function and level of activity prior to initiating treatment and at 0, 2, 4, 6, 12, and 24 weeks after starting treatment.

Pain will be assessed using the of the foot function index pain subscale (FFI-P) and the subject reported outcome measures (SROM). These two instruments have been used to assess pain in previous studies of plantar fascia treatments. (Please see Appendices 1-D and 1-E of the Protocol.)

Function will be assessed using two validated PRO instruments the PROMIS PF CAT and the FAAM. The PROMIS PFCAT is a subject relevant outcome measure that uses computer adaptive survey questions to assess the patient's pain and function in relation to daily activities. (Please see Appendix 1-A of the Protocol.) The FAAM has been shown to be a reliable, responsive, and valid measure of physical function for individuals with a broad range of musculoskeletal disorders of the lower leg, foot, and ankle. (Please see Appendix 1-B of the Protocol.)

Level of Activity will be assessed using the activity subscale of FAAM. This subscale scores quantitatively the level of difficulty subjects often face when they perform basic activities of daily living. It has shown to be an accurate and reliable predictor of the activity level while performing day-to-day activities. (Please see Appendix 1-B of the Protocol.)

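### The SAP names no ITU-versus-sham test on any outcome, and the protocol's between-group plan names a paired t-test that does not fit independently randomised arms

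*SAP*

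**What the plan says.** **Protocol.** The principal aim, under Patient Reported Outcome Measures (Aim 1), is comparative: "The principal aim of this study is to compare the efficacy of treatment and time course of response to treatment between the two groups". The Lay Summary is the only place that declares a primary outcome: "The primary outcome measure will be a computer adaptive questionnaire where pain, function and level of activity will be compared between the two groups". One instrument is described in those terms: "The PROMIS PFCAT is a subject relevant outcome measure that uses computer adaptive survey questions". Aim 2 compares change in plantar fascia thickness between the arms.

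Under Statistical analysis the protocol states: "FFI-P, PFCAT, and FAAM scores before and after intervention will be compared between the two groups using a paired t-test". For imaging, "the mean thickness of the plantar fascia will be compared between the two groups before and after treatment", again by paired t-tests. Randomization and Blinding describes individual 1:1 allocation with no matching. Target enrolment is 50.

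**SAP.** It covers three outcomes: a 0 to 10 pain score, hypoechoic lesion volume and the Foot Function Index (FFI) pain subscale. For pain it calculates, in each arm, the percentage of subjects who met a 25% reduction goal. Lesion volume and mean FFI are set against their baseline values. Statistical Calculations names one test: "Student T-tests were utilized to determine statistically significant differences between baseline and subsequent follow-up measurements", at a 0.05 level. It does not say whether the test is paired or run separately by arm.

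**The concern.** The trial's question is whether ITU added to standard of care does better than sham added to standard of care. The SAP's test asks whether scores moved from baseline. Both arms receive NSAIDs, heel cups and physical therapy. The protocol's own Background reports that initial conservative management treats symptoms effectively in 90% of patients in under 12 months. Improvement is therefore expected in both arms even if ITU does nothing, and significance against baseline cannot be read as benefit over sham.

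The protocol does not fill the gap, because the test it names does not fit two independent groups. Followed as written, the two documents leave Aims 1 and 2 without a valid efficacy test. A reader of the SAP also cannot tell how the outcome the Lay Summary calls primary, or the thickness outcome of Aim 2, is to be analysed.

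**Working it through.** The plan states no power or sample-size calculation, so there is no figure to reproduce. The point rests on the text; the arithmetic only shows scale.

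**1. Outcome by outcome.**

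| Outcome | Protocol | SAP |
|---|---|---|
| PROMIS PF CAT | Between groups, paired t-test | Not mentioned |
| FAAM | Between groups, paired t-test | Not mentioned |
| FFI pain | Between groups, paired t-test | Against baseline |
| Fascia thickness | Between groups, paired t-tests | Not mentioned |
| Lesion size | Recorded; no test stated | Volume against baseline |
| 0 to 10 pain, 25% goal | Goal not found in the supplied text | Percentage in each arm, no test; scores against baseline |

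No row has a valid between-arm test.

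**2. What a paired t-test can mean here.**
- Before against after within one arm is not an ITU-versus-sham test.
- Across arms, no pairs exist. If equal arms were paired at random, the error rate would stay near 5% (5.0% to 5.2% in simulation), but the p-value would depend on the draw. In one simulated data set, 95% of re-pairings gave p between 0.10 and 0.26, against 0.18 for the two-sample test. Unequal arms could not be fully paired.
- It may be a misnamed two-sample test on per-subject change, which would be valid.

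**3. Why a baseline test cannot answer the question.** Let c be the change shared by both arms and e the ITU effect. The ITU arm's mean change estimates c + e, and sham's estimates c. A baseline test in the ITU arm tests c + e = 0. Only the difference between arms isolates e.

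**4. Illustration.** Assumptions, none of them in the documents: 25 per arm with no dropout, e = 0, a paired test run by arm, two-sided 0.05, and a true change of d SDs of change. Power in the direction of improvement, p, comes from a noncentral t with 24 df, noncentrality d × √25 = 5d and critical value 2.064. The chance that ITU is significant and sham is not is p(1 − p).

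| d | p | p(1 − p) |
|---|---|---|
| 0.3 | 0.302 | 0.211 |
| 0.6 | 0.821 | 0.147 |
| 0.8 | 0.970 | 0.029 |
| 1.0 | 0.998 | 0.002 |

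A direct two-sample test would wrongly favour ITU 2.5% of the time. If the SAP's test were unpaired, p at d = 0.6 would be about 57% or 28%, for a baseline to follow-up correlation of 0.5 or 0.7, instead of 82%.

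**5. What a between-arm test can detect with 25 per arm.** The noncentrality is d × √(25/2) = 3.536d with 48 df. Power reaches 80% at d = 0.81 SD of the measure analysed. ANCOVA divides the noncentrality by √(1 − r²) and has 47 df. That gives 0.70 SD of the follow-up score at an assumed baseline correlation r = 0.5, and 0.58 SD at r = 0.7.

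**6. Visits.** The SAP uses weeks 4, 8, 12 and 26. Table 1 has follow-up at weeks 2, 4, 6, 12 and 24, with no ultrasound at week 24, whereas the SAP images lesions at every follow-up. Weeks 4 and 12 agree. Week 26 may be the 24-week or 6-month contact.

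**The case against.** **The protocol does plan a between-group comparison, and the word paired may be a slip.** This is fair. Diagnostic Ultrasound (Aim 2) says change in thickness from baseline will be calculated, which fits a two-sample test on change. A reader might infer that no between-arm analysis was ever intended, and the documents do not support that. But the wrong test is named for both the questionnaires and thickness, and the SAP does not correct it.

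**Silence is not conduct.** A reader might infer that the randomised comparison was never made, or that the primary outcome and thickness went unanalysed. The documents do not show this. The SAP does not provide for these analyses, and nothing supplied says that it replaces the protocol's list. The front of the SAP and the separate ITU protocol listed in Section 4 were not available for review, and the SAP's citations begin at 7, so it may be part of a longer text.

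**The primary outcome is thinly declared.** It appears only in the Lay Summary. PROMIS PF CAT is an inference from the description: the protocol assigns pain to FFI-P and SROM, and for activity "Level of Activity will be assessed using the activity subscale of FAAM". Aim 1 ranks no instrument, and FFI pain is in the SAP. So the instrument needs confirming; it cannot be asserted.

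**Self-reported measurements in the SAP's test sentence could include PF CAT and FAAM.** The SAP describes only two self-reported measures, the pain score and FFI pain. Even on the wide reading, the test is still against baseline.

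**It is a pilot.** Efficacy is still its stated primary objective, and a pilot can report an arm difference with an interval.

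**Conclusion.** The point stands and must be fixed. The supplied SAP names no between-arm test on any outcome, and the protocol's named test is not valid for independent arms unless it is read as a misnamed two-sample test on change. The SAP text also omits PROMIS PF CAT, FAAM and thickness. This follows from the wording and depends on no assumed effect size.

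The size of the consequence is not fixed by the documents. A reader might infer a specific inflated false-positive rate, but that requires a paired test run by arm, an assumed change, and a rule of claiming efficacy when ITU is significant and sham is not. The SAP states none of these. Even under that rule the rate runs from about 21% at 0.3 SD down to 0.2% at 1.0 SD. These rates illustrate the problem; they are not estimates for this trial.

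**What to change.** - Base efficacy on ITU versus sham at one named visit, with an estimate and 95% confidence interval. ANCOVA adjusted for baseline is preferred; a two-sample test on change would also cure the error. Week 12 appears in both documents and has questionnaires and ultrasound in Table 1.
- Keep the tests against baseline as descriptive only.
- Have the sponsor confirm the primary instrument and analyse it as primary, or disclose that it was replaced or not collected.
- Report thickness, FAAM, FFI pain and lesion volume with between-arm estimates. Report the 25% responder result as a difference between arms with a 95% confidence interval.
- The SAP is in the past tense. Make the change as a dated note, and label any choice made after seeing data, including the visit, as post hoc.
- Reconcile SAP weeks 8 and 26 and the imaging visits with Table 1.

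The cost is a dated note covering both documents. No new data are needed if PROMIS PF CAT was collected as scheduled, which the SAP does not confirm. The price is precision: with 25 per arm, only differences of about 0.81 SD unadjusted, or less with baseline adjustment, are detectable with 80% power, so the result may be inconclusive.
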